 5 CPK, Alkaline Phosphatase, total and direct bilirubin, albumin, total protein), CBC
 6 (hematocrit, hemoglobin, white blood cell count and differential, platelet count).
 7 6) Extended blood panel: alpha fetoprotein, gGT, immunoglobulins, rheumatoid factor, ANA,
 8 SMA, lipid panel, INR, reticulocyte count, ESR.
 9 7) 50 mL of blood in heparinized green top tubes for NK and T cell analysis.
 10 8) HBV DNA viral load, HBeAg, anti HBe, HBsAg, and anti HBs levels and quantitative HBe and
 11 HBs measurement
 12 9) Blood sample for storage (10 mL of serum and 10 ml of plasma stored frozen in 0.5-1.0 mL
 13 aliquots)
 14 10) Fibroscan
 15

16 **Table 1: List of study related procedures**
 17

Procedure	Screen	Pre-Rx biopsy	Day 0	Wk 2, 4, 8	Wk 12	Week 24 End of Rx	Post-Rx wk 12, 24, 36	Post-Rx wk 48, End of Study
H&P/breif clinical evaluation, compliance, AE, concomit. drugs, etc	X	X	X	X	X	X	X	X
Symptom questionnaire	X	X	X	X	X	X	X	X
Visual Analog Scale	X	X	X	X	X	X	X	X
Promis 7	X	X	X	wk 2		X		X
Chem 20	X	X	X	X	X	X	X	X
CBC	X	X	X	X	X	X	X	X
Anti-HAV	X							
HBsAg	X	X	X	X	X	X	X	X
HBsAg quantitative			X		X	X		X
anti-HBs	X							
HBeAg	X	X	X	X	X	X	X	X
HBeAg quantitative			X		X	X		X
anti-HBe	X							
anti-HBc	X							

anti-HCV	X							
IL28B	X							
HBV DNA	X	X	X	X	X	X	X	X
AFP	X							X
gGT	X							X
Immunoglobulins	X							X
rheumatoid factor	X							X
ANA	X							X
SMA	X							X
Lipid panel	X							X
thyroid panel	X				TSH	TSH		
INR	X							X
reticulocyte	X							X
ESR	X							X
storage - 5mL serum and 5mL plasma	S&P	Serum	Serum	S&P	S&P	S&P	S&P	S&P
Immunology - 50mL	X	X	X	X	X	X		X
Urine pregnancy	X		X	X	X	X		
UA	X					X		
Urine creatinine, phosphate, beta-2-microglobulin						X		
Liver Biopsy		X	Time d					
Abdominal u/s		X						
CXR		X						
EKG		X						
Fibroscan	X							X

1

2

3

4

5

ASSESSMENT OF RESPONSE

6

Clinical Definitions

7

8

a) **Loss of HBeAg (HBeAg-positive patients only):** loss of detectable HBeAg with or without anti-HBe seroconversion confirmed on 2 consecutive visits at least 12 weeks apart.

9

10

b) **Loss of HBsAg:** Loss of HBsAg, with or without anti HBs seroconversion confirmed on 2 consecutive visits at least 12 weeks apart.

11

- 1 c) **Sustained response:** virological, serological, biochemical, or combined response present at
2 the time of last observation and at least six months after stopping therapy.

3

4

5 The primary goals of this study are centered on understanding the mechanisms, and identification of

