6 predictive factors associated with a favorable response to peginterferon therapy when added on to
7 long-term NUCs treatment, in patients with HBeAg positive and negative chronic HBV infection.

8

9 **Primary end-points**

10

- 11 1) The primary end-point for this study will be the change in level of ISG expression and NK cell
12 responses before and after 1st peginterferon injection in responders versus non-responders
13 to peginterferon add-on therapy.
- 14 2) Proportion of eAg positive patients showing eAg loss with or without seroconversion at end
15 of treatment and 24 and 48 weeks off therapy.
- 16 3) Proportion of eAg positive patients showing sAg loss with or without seroconversion at end
17 of treatment and 24 and 48 weeks off therapy
- 18 4) Proportion of eAg negative patients showing sAg loss with or without seroconversion at at
19 end of treatment and 24 and 48 weeks off therapy

20

21 **Secondary endpoints**

22

- 23 1. Level of qHBsAg decline at treatment week 12, at end of treatment and 24 and 48 weeks off
24 therapy, compared to pretreatment levels in eAg positive and negative patients
- 25 2. Level of qHBeAg decline at treatment week 12, at end of treatment and 24 and 48 weeks off
26 therapy, compared to pretreatment levels in eAg positive and negative patients
- 27 3. Correlation of qHBsAg levels at initial evaluation, week 12,24,36 and 48 with intrahepatic
28 pregenomic and cccDNA concentration before and after initiation of peginterferon in
29 responders versus non-responders to treatment.
- 30 4. Intrahepatic pregenomic and cccDNA concentration before and after starting treatment with
31 peginterferon.
- 32 5. Epigenetic alterations in HBeAg positive and negative patients following first 1st
33 peginterferon injection compared to pretreatment levels as measured by chromatin
34 immunoprecipitation (ChIp) assays

- 1 6. Frequency and functional activity of circulating and liver infiltrating, HBV-specific T-cells,
2 measured before and during treatment in responders versus non-responders to
3 peginterferon add-on therapy.
4

5 DOSE CHANGES 6

7 **Stopping peginterferon therapy:** 8

9 Add-on peginterferon will be discontinued early for any of the following reasons:

- 10 a) **Toxicity**- the dose of peginterferon will be modified or discontinued according to Table 1:
11 Peg-Interferon Alfa-2a Dose Modification Guidelines (see below).
12 b) **Withdrawal of informed consent** (subject's decision to withdraw for any reason.

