13 c) **Any clinical adverse event, laboratory abnormality, or intercurrent illness**, which in the
14 opinion of the investigator indicates that continued participation in the study is not in the
15 best interest of the subject. If any of the following laboratory or clinical criteria is obtained
16 for any subject, the result must be repeated/confirmed within 72 hours. If the results are
17 confirmed, the subject must discontinue treatment. Clinical criteria must have Principal
18 Investigator or Sub-Investigator assessment prior to permanent discontinuation.
- 19 – Evidence of confirmed hepatic decompensation (Child-Pugh Class B or C, Score > 6)
20 (discontinue all treatment);
 - 21 – Platelets < 25 x 10⁹ cells/L;
 - 22 – Hemoglobin <8.5 g/dL
 - 23 – Absolute neutrophil count < 250 mm³/ml
 - 24 – Severe neuropsychiatric signs and symptoms (including depression) for both new and
25 worsening events that are considered clinically significant by the investigator.
26
- 27 d) **Pregnancy** women of childbearing potential must contact the investigator or study staff
28 immediately if they suspect they might be pregnant (eg, missed or late menstrual period) at
29 any time during study participation. If subjects become pregnant the research staff will stop
30 peginterferon, but subjects may continue taking their antiviral oral agent at the discretion of
31 the study doctor. The investigator will discuss possible management options with the
32 subject. Subjects who do become pregnant will continue to be followed for the outcome of
33 the pregnancy. The NIH will not cover any aspects of obstetrical, child or related care.
34

- 1 e) **Loss of ability to freely provide consent** through imprisonment or involuntary
 2 incarceration for treatment of either a psychiatric or physical (eg, infectious disease) illness.

3

4

5 **Stopping NUCs therapy**

6

7 Treatment with NUCs will be stopped under the following conditions

- 8 a) HBeAg loss, with or without anti HBe seroconversion, in eAg positive patients, that is
 9 confirmed on 2 separate tests, at least 6 months apart.
 10 b) HBsAg loss, with or without anti HBs seroconversion, that is confirmed in 2 separate tests, at
 11 least 6 months apart.

12

13

14

15 **Peginterferon Dose Modifications**

16

17 Dose modification of peginterferon α -2a should be managed according to Table 2. This table is based
 18 on recommendations from the peginterferon α -2a package insert, and have been modified as

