 19 necessary for this study. As Tables 2 is a guideline, investigators may modify the dose based on
 20 clinical judgment.

21

22

23

Table 2: Peg-Interferon Alfa-2a Dose Modification Guidelines

Laboratory Value/Clinical Criteria:	Dose Modification:	Additional Instructions:
ANC:		
$\geq 0.75 \times 10^9$ cells/L	Maintain at 180 μ g	
$\geq 0.25 \times 10^9$ to $< 0.75 \times 10^9$ cells/L	Reduce to 135 μ g	
$< 0.25 \times 10^9$ cells/L	All study drugs should be interrupted until ANC values return to more than 1000/mm ³	Reinstitute at 90 μ g and monitor ANC
Platelets:		

$\geq 50 \times 10^9$ cells/L	Maintain at 180 μ g	
$\geq 25 \times 10^9$ to $< 50 \times 10^9$ cells/L	Reduce to 90 μ g	
$< 25 \times 10^9$ cells/L	Discontinue all study drugs if value is confirmed	Treatment should not be reinstated
ALT:		
ALT $> 10 \times$ ULN	Reduce to 135 μ g or interrupt all study drugs if repeated ALT results are $> 10 \times$ ULN	If ALT increases are progressive or there is evidence of hepatic decompensation therapy should be interrupted
New Ocular symptom(s):		
New decrease or loss of vision or other clinical significant ocular sign or symptom	Interrupt all study treatment	Complete eye examination must be performed.
New or Worsening Neuropsychiatric Signs or Symptoms (Including Depression):	Mild No change Evaluate weekly by visit or phone until symptoms improve.	Evaluate weekly (with visit at least every other week). Consider psychiatric consultation if no improvement. If improved and stable for 4 weeks, may resume normal dosing.
Moderate	Reduce dose to 135 μ g	
Severe	Discontinue all study drug treatment	Psychiatric therapy necessary. Treatment should not be reinstated.
Creatinine Clearance (CrCl):		
< 30 mL/min	Reduce to 135 μ g	
Hemodialysis	Reduce to 135 μ g	

1 Source: adapted from Pegasys® package insert.

2

3

STATISTICAL ANALYSIS

Power calculation

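### A confirmed neutrophil count below 0.25 x 10^9/L means discontinue under stopping item c but interrupt and re-start under Table 2, and neither rule is given precedence

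*Combined protocol and SAP*

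**What the plan says.** Three places in the Dose Changes section bear on a very low neutrophil count.

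- **Stopping peginterferon therapy, item c.** The list includes "Absolute neutrophil count < 250", with the unit printed as mm³/ml. If a listed criterion is met "for any subject, the result must be repeated/confirmed within 72 hours", and if the results are "confirmed, the subject must discontinue treatment". Item c has no provision for re-starting.
- **Table 2, lowest neutrophil row (below 0.25 x 10^9 cells/L).** The action is "All study drugs should be interrupted until ANC values return to more than" 1000/mm³. The additional instruction begins "Reinstitute at 90" µg and asks for the count to be monitored.
- **Text on which rule applies.** Item a sends toxicity to the dose table: "the dose of peginterferon will be modified or discontinued according to Table 1". The Peginterferon Dose Modifications section says the table should be followed, then adds "As Tables 2 is a guideline, investigators may modify the dose based on" clinical judgment.

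Separately, the Initiation of Treatment section allows peginterferon to be re-started once an adverse event resolves and the patient agrees. It makes no exception for the criteria in item c.

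**The concern.** The same confirmed laboratory result leads to two actions that cannot both be followed. Under item c the patient comes off peginterferon; under Table 2 the patient goes back on it after recovery. One investigator could end treatment and another resume it, each citing the protocol. Under the protocol's own definition of a deviation, resuming under Table 2 could also be recorded as a departure from item c.

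What is at stake is patient safety and consistent conduct. The Hazards section names low white-cell and granulocyte counts as the most frequent marrow findings and says interferon may raise susceptibility to infection. The exclusion criteria set floors for platelets and haemoglobin but none for neutrophils.

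The early mechanistic measurements are not at risk. The liver gene-expression sample at 6 hours and the NK-cell samples at 6 and 24 hours follow the first injection and precede any such decision. An effect on responder classification could arise only indirectly, through later exposure, and the documents do not allow it to be quantified.

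**Working it through.** The plan gives no figure of its own to reproduce here. The check compares texts, with a unit conversion and a count of injections.

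**1. Is the trigger the same?** The unit printed in item c is not a count unit. Appendix 1 pairs 500/mm³ with 0.50 GI/L, so 250/mm³ = 250 x 10^6/L = 0.25 x 10^9/L, which is Table 2's cut-off with the same strict inequality. Read instead as 250 per mL, the threshold would be 0.00025 x 10^9/L, 1000 times lower, so the per-mm³ reading is used. Every confirmed count below the cut-off then meets both rules.

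**2. Are the actions different?** Item c appears under reasons for early discontinuation. Table 2 uses interrupting and discontinuing as distinct actions: its lowest platelet row discontinues with no reinstatement, whereas its lowest neutrophil row interrupts and reinstitutes.

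**3. How do item c's five criteria compare with Table 2?**

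| Criterion in item c | Table 2 |
|---|---|
| Platelets | Agrees: discontinue, no reinstatement |
| Severe neuropsychiatric events | Agrees: discontinue, no reinstatement |
| Haemoglobin | No row, so no competing rule |
| Neutrophils | Differs: interrupt, then reinstitute |
| Hepatic decompensation | Wording differs: item c ends all treatment; the ALT row interrupts |

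That is 2 + 1 + 2 = 5. Only the neutrophil row expressly orders re-starting against item c.

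**4. Is precedence stated?** No. Item a defers to the dose table, item c is mandatory, and the table is described as a guideline. No sentence ranks them.

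**5. How much treatment is in dispute for one patient?** Take weekly doses at weeks 0 to 23 and detection before that week's dose at a scheduled visit:

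- week 2: 24 − 2 = 22 remaining (92%)
- week 4: 24 − 4 = 20 (83%)
- week 8: 24 − 8 = 16 (67%)
- week 12: 24 − 12 = 12 (50%)

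Read as final, item c gives none of these. Table 2 allows those left after recovery, so each figure is an upper bound.

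**6. How often?** The documents give no rate. As an assumption, let neutrophils fall in proportion to the 20–50% white-cell fall in the Hazards section. The baseline count needed to reach the cut-off is 0.25/(1 − 0.20) = 0.3125, or 0.25/(1 − 0.50) = 0.50, x 10^9/L. Only patients starting below those values would cross it.

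**7. Related wording.** Item a's reference is to the wrong number: the protocol has "Table 1: List of study related procedures", and the dose table is Table 2. The general re-start sentence is not made subject to Table 2's no-reinstatement rows. It is also undefined whether *all study drugs* includes the nucleos(t)ide analogue (NUC). Initiation of Treatment continues the NUC through follow-up, the section on stopping NUCs lists only confirmed antigen loss, and item d (pregnancy) treats the oral agent separately.

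**The case against.** The best counter-argument is that the text can be read as one scheme. Initiation of Treatment says peginterferon may be stopped under the stopping rules and later re-started. On that reading item c stops the drug and Table 2 says where re-starting is allowed. The sentence in item c that calls discontinuation permanent concerns clinical criteria, and a neutrophil count is a laboratory one. Alternatively, a mandatory rule outranks a guideline, so item c prevails.

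Each reading is arguable, but neither is written, and they give opposite answers. Applied generally, the re-start sentence would also override Table 2's own no-reinstatement rows. The mandatory-over-guideline reading competes with item a, which makes the table the basis for modifying or discontinuing for toxicity. A third reading, interrupting until confirmation and discontinuing after it, is not stated either: the neutrophil row does not mention confirmation, although the platelet row does.

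Several narrower points do stand:

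- The hepatic instructions may be compatible, since one concerns confirmed decompensation and the other evidence of it.
- Item a gives the dose table's correct title, so the misnumbering is unlikely to mislead.
- Patients are treated at one centre with weekly review of all study patients, which makes divergent practice less likely.
- The section on protection against risks promises blood counts every 2 weeks, so detection could come after week 12 with fewer than 12 injections left.
- The white-cell fall is described as typical and is a weak basis for judging extreme neutrophil counts.

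These limit the size of the problem; they do not remove the contradiction.

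**Conclusion.** The concern holds. At one confirmed laboratory value, two safety rules give incompatible instructions on re-starting peginterferon, and the protocol does not say which governs. The text is wrong as written, not merely short of detail, and needs correcting even though the event is probably uncommon.

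The disputed treatment is at most 22, 20, 16 or 12 of 24 injections for detection at week 2, 4, 8 or 12, and less for later detection or slow recovery. The conclusion assumes that item c's malformed unit means cells per mm³; the injection counts also assume that item c's discontinuation is final. No event rate is assumed, and no effect on the early gene-expression or NK-cell measurements is claimed. The hepatic wording, the table number and the undefined drug term are secondary, and the conclusion does not depend on them.

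**What to change.** In one amendment, reconcile item c and the lowest neutrophil row of Table 2 so that a confirmed count below 0.25 x 10^9/L leads to one action. Correct the neutrophil unit in item c and the table number in item a.

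As secondary items in the same amendment:

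- say whether the general re-start sentence is subject to Table 2's no-reinstatement rows, or otherwise reconcile them;
- reconcile the two hepatic decompensation instructions;
- define whether the study drugs referred to in Table 2 include the NUC.

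Which action applies is for the investigators and the IRB to decide. The cost is wording only, with no added visits, samples or patients.

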NUCs with potent activity against the HBV reverse transcriptase and high barrier to resistance have been very effective at suppressing viral replication and were shown to be associated with improved clinical outcomes including reversal of cirrhosis [7, 8]. However, discontinuing therapy after one year is associated with high relapse rates and therefore most patients require long-term therapy to maintain suppression of viral replication [9-11]. Even with long-term use of NUCs, only about 50% of persons who were initially HBeAg positive undergo HBeAg seroconversion (the endpoint of therapy for HBeAg positive persons) [12, 13] and among those who were initially HBeAg negative, only about 1%-2% experience HBsAg seroconversion (the endpoint of therapy for HBeAg negative persons) [14, 15] Unfortunately, there are substantial costs associated with long-term therapy and there is the potential for serious side effects including renal toxicity and possibly loss of bone mass [16-20] Thus, new agents or approaches are needed to manage patients with chronic HBV infection. One approach that has been taken to improve HBsAg loss was to combine the two most potent NUCs. In one notable trial, the efficacy and safety of entecavir monotherapy was compared to the combination of entecavir and tenofovir in persons with HBeAg positive and negative chronic HBV infection. After 96 weeks of therapy, a comparable proportion of patients in each study arm achieved the primary end point of a level of HBV DNA < 50 IU/mL (83.2% vs 76.4%, respectively), indicating no benefit of a combination NUC approach over potent monotherapy [21]. Another approach was to combine a nucleoside analogue with peginterferon. This strategy is theoretically appealing as the combined effect of peginterferon, an immunomodulator, and a nucleos(t)ide analogue, a potent inhibitor of viral replication, may result in a synergistic anti-viral effect. However, several trials comparing the efficacy of combination peginterferon-NUCs therapy to either agent alone failed to show a clear advantage of combination therapy over either agent alone. Four randomized controlled trials comparing peginterferon alfa and NUCs (either lamivudine or adefovir) to peginterferon alone or NUCs alone have been conducted in persons with HBeAg positive and negative chronic HBV infection. [22-25]. All

14

15

16

17

18

19

20

21

22

23

24

25

26

27

28

29

30

31

32

33

34

35

36

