3. To identify pre- and on-treatment predictors of serological response to peginterferon add-on/nucleos(t)ide combination therapy.
4. To determine if there are differences in epigenetic regulation of cccDNA between HBeAg positive and negative CHB at baseline and following a single dose of peginterferon treatment

PROTOCOL OVERVIEW

We intend to enroll a total of 60 patients with HBeAg positive (n=30) and HBeAg negative (n=30) chronic HBV infection, who have been on-treatment with one or more nucleos(t)ide analogues for at least 192 weeks prior to study enrollment with maintained viral suppression (HBV DNA level <100 IU/ml). After a thorough medical evaluation and liver biopsy, participants will receive therapy with subcutaneous injections of peginterferon-alpha 2a at a dose of 180mcg per week for a total of 24 weeks. A second liver biopsy will be performed 6 hours following the first peginterferon injection for the purpose of assessing ISGs, intrahepatic NK cell quantity and function and intrahepatic viral biomarker response patterns. Most interferon induced genes achieve maximal response in the liver and periphery within 4 hours, begin to decline by 8 hours, and return to baseline levels by 24 hours post-administration of interferon. Because peginterferon is slower to be absorbed we have selected the six hour rather than a four hour time point.[38]

1 Patients will be followed carefully on weeks 0, 2, 4, 8, 12 and 24 during treatment and at 12 week
2 intervals thereafter until 48 weeks post-treatment.
3 During study visits patients will be assessed for compliance with study medications, as well as the
4 development of any treatment related side effects and/or adverse reactions. In addition, blood will
5 be drawn periodically for the assessment of routine blood tests, quantitative viral biomarker levels,
6 serological response markers and immune cell functional status.
7

8 **INCLUSION/EXCLUSION CRITERIA** 9

10 **Inclusion criteria: HBeAg positive group**

- 11
- 12 1) Age >18 years and older, male or female.
- 13 2) Known serum HBsAg and HBeAg positivity at the time of screening.
- 14 3) Ongoing treatment with one or more NUCs for at least 192 weeks before study entry.
15 Subjects may have a brief interruption of treatment for medical reasons (e.g. breast feeding)
16 not to exceed 8 weeks and none within the 48 weeks before study entry.
- 17 4) HBV DNA levels <100 IU/mL, measured at least 12 months prior to, and upon enrollment to
18 the study.

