- 19 5) ALT level ≤ 2 ULN based on at least two determinations taken at least one month apart
20 during the 24 weeks before study entry with the second being at time of screening
- 21 6) Written informed consent

22

23 **Inclusion criteria: HBeAg negative group**

- 24
- 25 1) Age >18 years and older, male or female.
- 26 2) Known serum HBsAg positivity and HBeAg negativity at the time of screening.
- 27 3) Ongoing treatment with one or more NUCs for at least 192 weeks before study entry.
28 Subjects may have a brief interruption of treatment for medical reasons (e.g. breast feeding)
29 not to exceed 8 weeks and none within the 48 weeks before study entry.
- 30 4) HBV DNA levels <100 IU/mL, measured at least 12 months prior to, and upon enrollment to
31 the study
- 32 5) ALT level ≤ 2 ULN based on at least two determinations taken at least one month apart
33 during the 24 weeks before study entry with the second being at time of screening
- 34 6) Written informed consent

35

1 Exclusion criteria (for both eAg positive and negative patients)

- 2
- 3 1) Co-infection with HDV as defined by the presence of anti-HDV in serum and/or HDV antigen
- 4 in the liver.
- 5 2) Co-infection with HCV as defined by the presence of HCV RNA in serum.
- 6 3) Co-infection with HIV as defined by the presence of anti-HIV in serum.
- 7 4) Decompensated liver disease as defined by serum bilirubin >2.5 mg/dL (with direct bilirubin
- 8 > 0.5 mg/dL), prothrombin time of greater than 2 seconds prolonged, a serum albumin of
- 9 less than 3 g/dL, or a history of ascites, variceal bleeding or hepatic encephalopathy.
- 10 5) Presence of other causes of liver disease, (i.e. hemochromatosis, Wilson disease, alcoholic
- 11 liver disease, severe nonalcoholic steatohepatitis defined as the presence of marked
- 12 ballooning injury on liver biopsy, alpha-1-anti-trypsin deficiency).
- 13 6) A history of organ transplantation or in the absence of organ transplantation, any
- 14 immunosuppressive therapy requiring the use of more than 5 mg of prednisone (or its
- 15 equivalent) daily.
- 16 7) Significant systemic illness other than liver diseases including congestive heart failure, renal
- 17 failure, chronic pancreatitis and diabetes mellitus with poor control, that in the opinion of
- 18 the investigator may interfere with therapy.
- 19 8) Pregnancy or inability to practice contraception in patients capable of bearing or fathering
- 20 children
- 21 9) Lactating women.

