23 peginterferon-alpha 2a (PEGASYS®, Roche), 180 mcg per week administered by subcutaneous
24 injection for a total of 24 weeks. Patients will continue treatment with their previous nucleosi(t)ide
25 analogue regimen during the treatment and follow-up phases of this study.

26 Patients will be seen in the outpatient clinic at weeks 2, 4, 8, 12, and 24, during treatment phase, at
27 12 week intervals thereafter up to 48 weeks post-therapy

28 Compliance will be monitored by medication diaries and counting of the residual vials returned at
29 outpatient visits. The side effects will be monitored regularly at each visit during the treatment phase
30 of the study by symptom questionnaires. Peginterferon alfa-2a will be dose reduced or stopped per
31 the dose reduction and stopping rules for peginterferon alfa-2a. Peginterferon alfa-2a treatment can
32 be restarted if the adverse event resolves and the patient is willing to re-start the medication.

33

34 **On-treatment liver biopsy**

35

1 At day 0, all patients will be readmitted to the NIH Clinical Center to start therapy with peginterferon
2 alfa-2a and to undergo a repeat liver biopsy. Biopsy will be scheduled at 6 hours following the first
3 injection of peginterferon, for the purpose of assessing ISG response pattern following the initial
4 exposure to peginterferon. Liver tissue will also be subjected to routine histopathological grading
5 and staging as well as for immune cell, quantitative viral kinetic and cccDNA epigenetic studies as
6 previously described.

7
8 Since the hypothesis to be tested in this study is that response to treatment peginterferon (i.e. loss of
9 HBeAg and HBsAg or both) is mediated by changes in hepatocyte gene transcription profile, it is
10 necessary to obtain liver tissue at two time points-before and 6 hours after the first dose of
11 interferon. Performing two liver biopsies within 12 weeks or even as short as 24 hours has been
12 performed in other Liver Disease Branch studies and has not been associated with an increase in the
13 complication rate or lower patient acceptance.

16 **Monitoring**

17 Day 0

- 18
- 19
- 20 1) Brief clinical evaluation
- 21 2) Review patient's eligibility for study
- 22 3) Symptom questionnaire
- 23 4) Visual analogue scale
- 24 5) Fatigue questionnaire (Promise 7)
- 25 6) Chemistry 20 (sodium, chloride, potassium, bicarbonate, calcium, phosphate, magnesium,

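### Responders are told to stop NUCs, against another section, with no blood test scheduled for about 12 weeks, no restart criterion, and some stops landing on the final visit

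*Combined protocol and SAP*

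**What the plan says.** Stopping NUCs therapy (under Dose Changes) states: "Treatment with NUCs will be stopped under the following conditions". Condition a) is "HBeAg loss, with or without anti HBe seroconversion, in eAg positive patients, that is" confirmed on two tests at least 6 months apart. Condition b) is HBsAg loss, with or without anti-HBs, confirmed over the same interval.

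Initiation of Treatment says that patients keep their previous "analogue regimen during the treatment and follow-up phases of this study". It does not mention the stopping rule.

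Peginterferon ends at week 24. After that, visits are at post-treatment weeks 12, 24, 36 and 48, the last being the final study visit. HBV DNA and ALT (within the chemistry panel) are scheduled at those visits and at no other time after week 24.

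The restart text concerns peginterferon: under Initiation of Treatment it can "be restarted if the adverse event resolves and the patient is willing to re-start the medication", and Table 2 covers resuming its dose. The ALT row of Table 2 and the decompensation criterion under Stopping peginterferon therapy direct staff to reduce, interrupt or discontinue drugs. Neither says when a NUC should be started again.

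**The concern.** A patient who meets the rule after week 24 has finished peginterferon and then stops the only remaining HBV drug. Viral return or an ALT flare could go untested until the next 12-week visit. When it is found, the protocol directs no action, so restarting becomes a case-by-case decision. If the rule is first met at the final visit, nobody looks again within the study.

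The protocol recognises the general hazard. The Background says that "discontinuing therapy after one year is associated with high relapse rates and therefore most patients require long-term therapy". Entry criterion 3 allows a past NUC interruption only if it was brief: "not to exceed 8 weeks and none within the 48 weeks before study entry".

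The concern is greatest for condition a). It covers patients who may still be HBsAg positive and who have not developed anti-HBe, although the Background names HBeAg seroconversion as the endpoint of therapy in HBeAg-positive disease.

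**Working it through.** There is no plan figure to reproduce. The check sets the stopping rule against the visit schedule.

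**Inputs.** Visits in weeks from first dose: 2, 4, 8, 12, 24 (end of peginterferon), then 36, 48, 60 and 72 (post-treatment weeks 12, 24, 36 and 48). Windows: ±3 days to week 24, ±5 days afterwards (Monitoring). Confirmation interval: at least 6 months (Stopping NUCs therapy). Six calendar months are at least 181 days, taken here as about 26 weeks.

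**Stop visit.** If loss is first seen at week w, the stop is the first scheduled visit at or after w + 26. Weeks left = 72 − stop week. Checks left = scheduled visits after the stop.

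| Loss first seen | w + 26 | Stop at week | Weeks left | Checks left |
|---|---|---|---|---|
| Weeks 2 to 8 | 28 to 34 | 36 | 36 | 3 |
| Week 12 | 38 | 48 | 24 | 2 |
| Week 24 (end of treatment) | 50 | 60 | 12 | 1 |
| Week 36 (post-treatment 12) | 62 | 72 (final visit) | 0 | 0 |
| Week 48 or later | 74 or more | rule not met | – | – |

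**Visit windows.** Visits 24 weeks apart are nominally 168 days apart. The widest windows give 168 + 3 + 5 = 176 days, or 168 + 5 + 5 = 178 days between two post-treatment visits. Both are short of 181, so windows do not let a 24-week pair qualify.

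**If 6 months is read as 24 weeks.** Each pattern moves one visit earlier: loss by week 12 leaves 3 checks, week 24 leaves 2, and week 36 leaves 1. Loss at week 48 then puts the stop at the final visit. Either reading therefore produces a final-visit stop.

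**Can the rule be met during peginterferon?** Antigens are also tested at the biopsy admission and on Day 0.

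- Patients have 12 weeks from eligibility to complete the biopsy and start peginterferon, so the admission is at most about 12 weeks before first dose.
- From there to week 12 is at most 12 + 12 = 24 weeks: 168 days, or 168 + 3 = 171 with the window. That is short of 181.
- Day 0 to week 24 is also 168 days, or 171 with the window.
- On scheduled tests the earliest possible stop is therefore week 24, from a first negative at the biopsy admission. An unscheduled test could bring it earlier, but that would be rare.

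**Gap after a stop.** Post-treatment visits are 12 × 7 = 84 days apart. With ±5 days at each end the gap is 84 − 10 = 74 to 84 + 10 = 94 days.

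**How many patients.** Power calculation gives target loss rates of 35% (HBeAg) and 30% (HBsAg), with 30 patients per group. 0.35 × 30 + 0.30 × 30 = 10.5 + 9.0 = 19.5 of 60 (32.5%). At the reference rates of 10% and 5%: 3.0 + 1.5 = 4.5 of 60 (7.5%). These count patients who lose antigen. The number who lose it early enough to stop in the study is smaller and cannot be derived, because the documents give no timing of response.

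**The case against.** The strongest reply is that the two sections conflict, and if Initiation of Treatment governs there is no off-NUC period in the study. That is possible. The stopping rule is the more specific text, so reading it as an exception is reasonable, but the protocol has to say so.

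Second, clinicians can test or restart on judgment, and data are reviewed weekly in research rounds. Those rounds review what has been collected and add no blood draw. The two-weekly tests mentioned under Protection against risks are blood counts, not ALT or HBV DNA. Unscheduled tests could shorten the gap, and could also bring a stop forward, but the plan provides for neither.

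Third, a reader might infer that a patient who stops at the final visit is left without care. The documents do not support that. The Recruitment Plan expects about 85% of patients from the branch's own clinic and names two other branch protocols, under which care may continue. What those protocols require after a NUC stop is not stated.

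Fourth, a reader might apply the Background's high relapse rates to these patients. That statement concerns stopping after one year of therapy. It does not cover confirmed antigen loss, and no rate is given for that case.

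Fifth, a reader might infer that NUC status at post-treatment week 48 would be unknown. Table 1 lists compliance and concomitant drugs at every visit, so it should be collected. Nor can anything be said about what patients are told, because the consent pages were not available.

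**Conclusion.** The point stands as a safety-monitoring gap that is cheap to close. Followed as written, the stopping rule and the visit schedule take some responders off all HBV drugs, with the first scheduled HBV DNA and ALT 74 to 94 days later and no written restart criterion. With 6 calendar months, three, two, one or no scheduled checks remain, depending on when loss was first seen. Loss first seen at post-treatment week 12 leaves none in this study.

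This assumes that the stopping rule overrides the continuation text, that stops are made at scheduled visits, and that no unscheduled tests are done. The 19.5 of 60 depends on the target rates being reached. It is not an upper bound, since the pilot study cited in the Background reported 60% HBsAg loss. It is also not the number who would stop.

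Two stronger statements should be avoided. One is that the rule can never be met before peginterferon ends: the pre-treatment antigen tests leave a rare exception. The other is that the antigen end-points are undermined, which nothing here shows.

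**What to change.** 1. In Initiation of Treatment, after the statement that NUCs continue, add: unless the NUC-stopping rule is met.
2. In Stopping NUCs therapy, add HBV DNA and ALT at about weeks 4 and 8 after a stop, followed by the planned visits. Add a restart criterion with thresholds set by the investigators. HBV DNA above 1,000 IU/mL on repeat is one example. The protocol uses that level only to exclude patients whose viral load exceeded it during a past interruption, so it is a starting point and not an established re-treatment threshold.
3. If the rule is first met at the final visit, do not stop NUCs under the protocol, or add one off-NUC check 12 weeks later.

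The cost is about two extra blood draws per patient who stops: 2 × 19.5 = 39, so about 40 in total if every patient who lost antigen at the target rates also stopped. A protocol amendment is needed, plus one later visit for final-visit stops if that option is chosen. Sample size, end-points and tests do not change.
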